7.6 Pregnancy

In the event of a positive pregnancy test, subjects must immediately discontinue protocol therapy and must be discontinued from the study. The Investigator must report the positive pregnancy test to the appropriate contact listed in protocol Section 7.4 within 1 working day of the site becoming aware of the pregnancy.

All subjects should be informed that contraceptive measures should be taken throughout the study and for 6 months after discontinuing study drug. Information regarding a pregnancy occurrence in a study subject and the outcome of the pregnancy will be collected. The Investigator must follow the pregnancy to completion and provide an update to AbbVie after delivery.

Male subjects should be informed that contraceptive measures should be taken by their female partners. If the subject's partner should become pregnant during the study, this should also be reported and data may be collected. In the event of pregnancy occurring in the partner of an enrolled subject, written informed consent for release of medical information from the partner must be obtained prior to the collection of any pregnancy-specific information and the pregnancy will be followed to outcome.

Pregnancy in a study subject is not considered an adverse event. The medical outcome for either mother or infant, meeting any serious criteria including elective or spontaneous abortion, is considered a serious adverse event and must be reported to AbbVie within 24 hours of the site becoming aware of the event.

8.0

TOXICITY MANAGEMENT AND DOSE MODIFICATIONS

For the purpose of medical management, all adverse events and laboratory abnormalities that occur during the study must be evaluated by the Investigator. The table of clinical toxicity grades modified from the NCI CTCAE Version 4.0 (available on the CTEP home page <http://ctep.cancer.gov>) is to be used in the grading of adverse events and laboratory abnormalities that are reported as adverse events, each of which will be followed to satisfactory clinical resolution.

A drug-related toxicity is an adverse event or laboratory value outside of the reference range that is judged by the Investigator or AbbVie as having a reasonable possibility of being related to protocol treatment. A toxicity is deemed "clinically significant" on the basis of the Investigator's medical judgment.

Dose reductions or delays should be made for the likely causative agent. If one of the agents should be stopped for any reason other than disease progression, the subject can continue on the other single agent alone at the same dose and schedule.

8.1 ABT-414/Placebo Toxicity Management

Subjects will be closely monitored for treatment-related adverse events, especially allergic reactions, during all infusions. For the initial ABT-414/placebo infusion, pre infusion vital signs will be taken and direct observation is required for the first 15 minutes of the infusion. Also for the initial ABT-414/placebo infusion, subjects must remain at the site for monitoring for 60 minutes post infusion. For subsequent infusions, post-infusion monitoring is not required; however, pre-infusion vital signs should still be taken. Longer observation periods and more frequent vital sign checks may be required in subjects who experience infusion reactions.

Institutional standards should be used to treat all allergic reactions.

Based upon results from the first clinical and preclinical safety pharmacology evaluation of ABT-414, experience with other inhibitors of *EGFR*, and experience with MMAF ADCs, potential toxicities may include fatigue, vomiting, thrombocytopenia, allergic reactions, rash, eye complaints, and liver function test abnormalities.

8.1.1 Dose Modifications for ABT-414/Placebo

For all observed toxicities, subjects should be assessed for inter-current illness or other causes and treated as appropriate.

Starting doses and suggested dose level reductions are shown in [Table 9](#), and subsequent subsections discuss when dose reductions should be considered or are required. More aggressive dose reductions are always allowed if the Investigator believes that it is in the best interest of the subject.

With the exception of ophthalmologic toxicities as described in [Section 8.1.2](#) and hepatic laboratory abnormalities as described in [Section 8.1.6](#), all dose reductions are permanent unless a toxicity initially attributed as potentially related to ABT-414/placebo is later re-attributed as not potentially related and discussed with the Neuro-Medical Oncology study chair, AbbVie Medical Monitor or their designee.

Table 9. ABT-414/Placebo Dose Modification Table during Chemoradiation and Adjuvant Phase

Dose Level	Dose	
	Chemoradiation Phase	Adjuvant Phase
Starting Dose	2.0 mg/kg	1.25 mg/kg*
1 st Reduction	1.5 mg/kg	1.0 mg/kg
2 nd Reduction	1.0 mg/kg	0.75 mg/kg
3 rd Reduction	-	0.5 mg/kg
	-	Discontinue

* If CTCAE Grade 3 eye toxicity is observed during the Chemoradiation Phase, then 1.0 mg/kg is recommended, but not required, as the starting dose for the Adjuvant Phase.

8.1.2 Ophthalmologic Toxicities

Microcystic keratopathy is a very common adverse effect of ABT-414, occurring in over 50% of subjects. Key elements in the overall management of microcystic keratopathy include subject education, use of prophylactic eye drops to reduce severity, supportive care measures, and careful ophthalmological monitoring to identify microcystic changes or steroid-related adverse effects and guide supportive treatment.

8.1.2.1 Ophthalmologic Monitoring and Prophylactic Eye Drop Use

As described in [Section 4.2](#), subjects will receive ophthalmological examinations at regular intervals throughout the study, and additional examinations may be done as needed. The ABT-414-TOE examinations are intended to systematically identify and grade objective findings of ABT-414-related eye toxicity and to assess for adverse effects potentially related to ocular steroid use.

Administration of prophylactic eye drops for 7 days is required with each administration of ABT-414/placebo, from 2 days prior until 4 days after drug infusion. A description of the steroid-potency levels and dosing schedule for each, as well as considerations for adjusting prophylactic eye drop levels or frequency based on ophthalmologic findings, is described in Section 5.5.

Prophylactic and symptomatic use of cold compresses over the eyes and ophthalmologic vasoconstrictors around the time of ABT-414 infusions is allowed, as it may reduce drug uptake in the cornea.

8.1.2.2 Treatment of Ophthalmologic Toxicity Once Symptoms Occur

Supportive care measures (e.g., lubricating eye drops, therapeutic bandage contact lenses, punctal plugs, antibiotic drops, etc.) play a pivotal role in ABT-414 treatment, as they can provide considerable relief for symptoms of ABT-414-related eye toxicity, including photophobia, blurry vision and eye discomfort. Therefore, supportive care measures should be used early and extensively to minimize the need for ABT-414 dose interruptions and dose reductions.

Once corneal microcysts have formed, there are no known therapies that can remove them from the cornea. Thus, only therapies that can control symptoms and promote healing are indicated. Use of steroid eye drops outside the prescribed prophylactic period is allowed but may not be the best strategy, as it may inhibit the healing process. Supportive care measures should be actively considered and fully utilized when symptoms of ABT-414-related eye toxicity occur, as they are the most effective way to manage eye symptoms and maximize ABT-414 dosing.

Use of supportive care measures should be individually tailored for each subject based on frequent monitoring by an ophthalmologist to inform the best treatment for the subject. The choice and timing of supportive care measures is not restricted by the study protocol, and all choices are at the discretion of the study investigator in consultation with the ophthalmologist as needed. Supportive measures can be used throughout the treatment cycle, including days on which prophylactic eye drops are used, and they may be initiated prior to the onset of symptoms at the discretion of the investigator.

Lubricating eye drops may be used liberally throughout treatment and are commonly prescribed prior to onset of eye symptoms.

Feedback from ophthalmologists with experience managing ABT-414 ocular toxicity suggest that use of therapeutic bandage contact lenses can have a major impact on improving eye

symptoms, including photophobia, blurred vision and various forms of eye discomfort, and thus minimize the need for ABT-414 dose interruptions and dose reductions. Therefore, use of therapeutic bandage contact lenses should be strongly considered whenever toxicity suggesting the need for ABT-414 dose modification is present, and they may also be used for lower grade symptoms.

8.1.2.3 Discussions with Subjects

It is important that subjects understand this toxicity and the importance of following the recommendations for the prophylactic eye drops and supportive care measures, as well as the rapid reporting of their symptoms. It is also important to let them know that at this time, in all of the subjects, symptoms have improved over time and there is no evidence to suggest that there is any permanent damage done to the cornea. It does take some time, however, for symptoms to resolve and thus an immediate reversal of symptoms should not be promised. At least 3 – 4 weeks must take place for the regeneration of the cornea; this is an approximate timeline for when symptoms should improve and corneal healing should take place. Tumor responses to ABT-414 have been sustained in subjects who require treatment holds for 4 or more weeks.

8.1.2.4 ABT-414 Dose Adjustment for Ophthalmologic Toxicity

Guidelines for ABT-414/placebo dose modifications for ophthalmologic toxicities considered by the investigator to be related to ABT-414 are shown in [Table 10](#). Decisions on dose adjustments will be based on CTCAE grades assigned by the Investigator (not on the ABT-414-TOE grades). Re-treatment at a lower dose of ABT-414 has generally resulted in less severe toxicities. However, it is important to fully utilize supportive measures as needed in order to minimize the need for dose interruptions and dose reductions.

If, after a dose reduction for ocular symptoms, changes in supportive care interventions lead to significant improvement in ocular symptoms for subsequent ABT-414/placebo doses, the ABT-414/placebo dose may be re-escalated to the previous higher dose at the discretion of the investigator after discussion with the Neuro-Medical Oncology study chair or his/her designee.

Table 10. Guidelines for ABT-414/Placebo Dose Interruption and Re-Initiation During Chemoradiation and Adjuvant Phase for Ophthalmologic Toxicities

Ocular Adverse Event CTCAE Grade [^]	ABT-414 / Placebo Dosing Modifications	
	Dose Interruption*	Dose Reduction*
1 – Asymptomatic or mild symptoms; clinical or diagnostic observations only; intervention not indicated [^]	
 • Not indicated 	
 • Not indicated
2 – Symptomatic; medical intervention indicated (e.g., topical agents); limiting instrumental ADL [^]	
 • Not indicated, but allowed at investigator's discretion • Investigator should fully utilize supportive care measures** as needed to manage ocular findings 	
 • Not indicated, but allowed at investigator's discretion • Investigator should fully utilize supportive care measures** as needed to manage ocular findings
3 – Decline in vision (worse than 20/40 but better than 20/200); limiting self-care ADL [^]	
 • Recommended but not required; at investigator's discretion to interrupt study drug until AE resolves to at least Grade 2 • Investigator should fully utilize supportive care measures** as needed to manage ocular findings 	
 • Recommended but not required; at investigator's discretion unless otherwise noted • Investigator should fully utilize supportive care measures** as needed to manage ocular findings
4 – Perforation or blindness (20/200 or worse) in the affected eye [^]	
 • Interrupt study drug until AE resolves to at least Grade 2 (required) • Investigator should fully utilize supportive care measures** as needed to manage ocular findings 	
 • Required if Grade 4 toxicity present despite full utilization of supportive care measures**

[^] Grading criteria shown are for the term "microcystic keratopathy." For other ocular adverse events considered by the investigator to be related to ABT-414, use the applicable CTCAE grading criteria for that term.

* If use of supportive measures reduces severity of eye toxicity, the lower CTCAE grade severity (the grade in the presence of ongoing supportive measures) may be used to guide potential dose modifications.

** Supportive care measures include but are not limited to lubricant drops, bandage contact lens, antibiotic drops, ointments, punctal plugs and sunglasses.

8.1.3 Severe Allergic Reactions (Grade 3 or Grade 4)

These require the immediate interruption of ABT-414/placebo treatment and discontinuation from the study. Appropriate medical therapy including epinephrine, systemic corticosteroids, intravenous antihistamines, bronchodilators, and oxygen should be available for use in the treatment of such reactions. Subjects should be carefully observed until the complete resolution of all signs and symptoms.

8.1.4 Moderate Allergic Reactions (Grade 1 or Grade 2)

These will also require the immediate interruption of ABT-414/placebo infusion. Once symptoms have resolved, retreatment is allowed with an infusion over 60 to 70 minutes. All subsequent infusions will also be administered over 60 to 70 minutes.

8.1.5 Dermatologic Toxicities

Subjects developing dermatologic toxicities while receiving ABT-414/placebo should be monitored for the development of inflammatory or infectious sequelae, and appropriate treatment of these symptoms initiated. In subjects with mild and moderate (Grade 1 or Grade 2) skin toxicity, treatment should continue without dose delay or modification. Treatment with topical and/or oral antibiotics should be considered.

If a subject experiences severe (Grade 3 or Grade 4) acneiform rash, ABT-414/placebo treatment adjustments should be made based on a discussion between the Investigator, the RTOG Neuro-Medical Oncology Study Chair and AbbVie Medical Monitor.

Subjects who experience a grade 3 or higher dermatological toxicity will be treated as following: The subject will require a dose interruption and ABT-414/placebo may be reintroduced at a reduced dose (per the guidance previously stated above) if the toxicity returns to \leq grade 1 within 4 weeks.

8.1.6 Hepatic Laboratory Abnormalities (ABT-414/Placebo)

Guidelines for ABT-414/placebo dose modifications related to hepatic laboratory abnormalities are presented in [Table 11](#).

Table 11. ABT-414/Placebo Dose Modification Guidelines for Hepatic Laboratory Abnormalities

Hepatic Laboratory Abnormality	ABT-414/Placebo
ALT or AST > 5 × ULN* but ≤ 20 × ULN (and TBL ≤ 2 × ULN)	
 • Hold drug regardless of assessed relationship to drug. See Section 8.4 for guidelines on repeat testing (ALT, AST, ALP, TBL) and evaluation. • Dosing may not be resumed until ALT and AST have recovered to ≤ 5 × ULN* • Dosing may be resumed at the same dose if ALT or AST was elevated >5 × ULN* for less than 2 weeks. Additionally, dosing may be resumed at the same dose if another likely cause has been identified. • Dosing must be resumed at a reduced dose (see Table 9)** if ALT or AST was elevated > 5 × ULN* for more than 2 weeks and no other likely cause has been identified. • Following dose reduction, if ALT and AST remain ≤ 5 × ULN* after 2 doses at the reduced dose level, then re-escalation to the previous dose is allowed at the investigator's discretion. • If a subsequent dose reduction is required due to hepatic laboratory abnormalities, then re-escalation is not allowed.
ALT or AST > 20 × ULN or ALT or AST > 3 × ULN and TBL > 2 × ULN	
Hold drug regardless of assessed relationship to drug. See Section 8.4 for guidelines on repeat testing (ALT, AST, ALP, TBL) and evaluation.
 
If another clear cause has been identified, drug may be resumed when ALT and AST ≤ 5 × ULN and TBL ≤ 2 × ULN
 
In general, if no other cause has been identified, drug should be permanently discontinued, and rechallenge not attempted.
 
Rechallenge can be considered after consultation with the sponsor if all of the following are met:
 
 • the subject has shown important benefit from the drug and other options are not available, • ALT and AST have recovered to ≤ 5 × ULN and TBL has recovered to ≤ 2 × ULN, • the subject has been informed of the potential risk and has consented to the rechallenge, • close follow-up of the subject is feasible.

ALP = alkaline phosphatase, ALT = alanine transferase, AST = aspartate transferase, TBL = total bilirubin

* If elevated at baseline, either 5 × the baseline value or 8 × ULN, whichever is lower.

** Unless the next planned dose is already a lower dose per the protocol (i.e., start of the adjuvant phase).

8.1.7 Other Toxicities

For all other toxicities considered by the investigator to be potentially related to ABT-414/placebo, the general guidelines to be used for dose interruptions and/or dose reductions are shown in Table 12.

Table 12. General Guidelines for ABT-414/Placebo Dose Interruptions and Re-Initiation During Chemoradiation and Adjuvant Phase (Except Ophthalmologic, Allergic, Dermatologic Toxicities and Hepatic Laboratory Abnormalities)

CTCAE Grade	ABT-414	
	Dose Interruption	Dose Reduction
Grade 1	Not indicated	Not indicated
Grade 2	Not indicated	Not indicated, but at investigator's discretion
Grade 3	Interrupt study drug until AE resolves to at least Grade 1 (or baseline if higher than Grade 1)	Recommended but not required; at investigator's discretion
Grade 4	Interrupt study drug until AE resolves to at least Grade 1 (or baseline if higher than Grade 1)	Required

8.2 Ocular Steroid Toxicity Management

Adverse effects related to ocular steroid use should be managed as clinically indicated in consultation with the ophthalmologist. The decision whether to continue prophylactic eye drops at the same steroid potency level should weigh both the potential benefits and risks of continuing treatment. As described in Section 5.5, prophylactic eye drops must be reduced to Level 1 (non-steroid drops) if there is evidence of ocular steroid-related toxicity in the complete absence of any corneal epithelial abnormalities on the ABT-414-TOE.

8.3 Temozolomide Toxicity Management

TMZ should be administered per the local prescribing regulations. If local prescribing information and the instructions in Section 8.3.1 or Section 8.3.2 conflict, then either local prescribing information or protocol language can be used at the discretion of the investigator.

See Section 8.4 for guidelines on repeat testing and evaluation of hepatic laboratory abnormalities regardless of the assessed relationship to study treatments.

8.3.1 Temozolomide During Concomitant Radiation Therapy

Prophylaxis against *Pneumocystis jirovecii* pneumonia (PCP) should be per local regulation guidelines for all subjects receiving concomitant TMZ and radiotherapy.

No TMZ dose reduction will be made, but delay or discontinuation of TMZ administration will be decided weekly according to hematologic and non-hematologic adverse events (AEs), as specified below.

If the administration of TMZ has to be interrupted, the radiotherapy will proceed normally. Missed doses of TMZ will not be made up at the end of radiotherapy. The total number of days and total dose of TMZ will be recorded on the eCRFs.

If one or more of the following are observed:

- ANC ≥ 0.5 and $< 1.5 \times 10^9/L$
- Platelet count ≥ 10 and $< 100 \times 10^9/L$
- Grade 2 non-hematologic AE considered possibly related to TMZ (except alopecia, nausea and vomiting while on maximal antiemetic therapy, and fatigue)

then treatment with concomitant TMZ will be withheld until all of the following conditions are met:

- ANC $\geq 1.5 \times 10^9/L$
- Platelet count $\geq 100 \times 10^9/L$
- Grade ≤ 1 non-hematologic AE (except alopecia, nausea and vomiting, and fatigue)

In case of hematologic AE as defined above, a complete blood count (CBC) should be performed at least twice weekly. In case of non-hematologic AE, the subject should be assessed at least weekly with relevant laboratory test(s). As soon as all of the above conditions are met, the administration of TMZ will resume at the same dose as used initially.

If one or more of the following are observed:

- ANC $< 0.5 \times 10^9/L$ (Grade 4)
- Platelet count $< 10 \times 10^9/L$ (Grade 4)
- Grade 3 or 4 non-hematologic AE considered possibly related to TMZ (except alopecia, nausea and vomiting unless the subject has failed maximal antiemetic therapy, and fatigue)

then treatment with concomitant TMZ should be stopped.

If the duration of radiotherapy exceeds 7 weeks, then concomitant treatment with TMZ should be stopped after 49 days of TMZ treatment.

Summary of Temozolomide Delay or Discontinuation During Concomitant Radiation Therapy

AE	Value	Action
ANC	≥ 0.5 and $< 1.5 \times 10^9/L$	Delay temozolomide until: ---ANC $\geq 1.5 \times 10^9/L$ ---Platelet $\geq 100 \times 10^9/L$ ---Non-hem AE \leq Grade 1
Platelet count	≥ 10 and $< 100 \times 10^9/L$	
Non-hematologic (except alopecia, nausea/vomiting unless on maximal antiemetic therapy)	NA	
ANC	$< 0.5 \times 10^9/L$	Stop concomitant temozolomide
Platelet count	$< 10 \times 10^9/L$	
Non-hematologic (except alopecia, nausea/vomiting)	NA	

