An interim efficacy analysis based on a data cut of 30 April 2019 was performed by the RTOG Independent Data Monitoring Committee (IDMC), at which time 346 OS events had been observed out of 639 subjects included in the main part of the study. The primary analysis of OS based on the Intent-to-Treat (ITT) population showed no difference in OS between groups, with a median OS of 18.9 vs. 18.7 months for ABT-414 and placebo, respectively. The weighted ($\rho = 0$, $\gamma = 0.2$) stratified log-rank test p-value (1-sided) was 0.628, and the observed hazard ratio (HR) (95% CI) for OS was 1.01 (0.82, 1.25). The median PFS was 8.0 vs. 6.3 months for ABT-414 and placebo, respectively, with a stratified log-rank test p-value (1-sided) of 0.029. The observed hazard ratio (HR) (95% CI) for PFS was 0.84 (0.70, 1.02). Preliminary analysis of demographic and clinical characteristics did not reveal any factors predictive of OS benefit for the addition of ABT-414 to standard RT/TMZ therapy.

Overall, 99.4% and 97.8% of subjects experienced at least 1 adverse event, and 87.3% and 62.3% experienced a Grade 3 or higher AE in the ABT-414 and placebo arms, respectively. Overall, 94.7% and 36.1% of subjects experienced at least 1 ocular adverse event related to corneal epitheliopathy, 61.0% and 0.6% experienced a Grade 3 or higher AE related to corneal epitheliopathy, and 11.8% and 0% discontinued study drug (ABT-414 or placebo) in the

ABT-414 and placebo arms due to corneal epitheliopathy, respectively. The most common (> 10%) events related to corneal epitheliopathy included keratopathy, vision blurred, photophobia, dry eye, eye pain, keratitis, and punctate keratitis. Excluding events related to corneal epitheliopathy, events for which the incidence in the ABT-414 group was $\geq 5\%$ greater than in the placebo group included thrombocytopenia, gamma-glutamyltransferase increased, aspartate aminotransferase increased, alanine aminotransferase increased, constipation, blood alkaline phosphatase increased, fatigue, and platelet count decreased. Excluding events related to corneal epitheliopathy, Grade 3 or higher events for which the incidence in the ABT-414 group was at least 5% and was $\geq 2\%$ greater than in the placebo group included thrombocytopenia, gamma-glutamyltransferase increased, and alanine aminotransferase increased.

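### Protocol 8.3.1: the summary table for temozolomide during radiation contradicts its text on fatigue, antiemetics, stopping and resuming, and one hold in the text has no effect

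*Protocol*

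**What the plan says.** Section 8.3.1 of the protocol gives the rules for holding, resuming and stopping TMZ during radiation twice, once as text and once as a summary table.

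**Text**
- Hold TMZ for "Grade 2 non-hematologic AE considered possibly related to TMZ (except alopecia, nausea and vomiting while on maximal antiemetic therapy, and fatigue", or for low neutrophils or platelets.
- Resume when counts have recovered and there is at most a Grade 1 "non-hematologic AE (except alopecia, nausea and vomiting, and fatigue". The instruction is: "As soon as all of the above conditions are met, the administration of TMZ will resume at the same dose as used initially".
- Stop TMZ for a Grade 3 or 4 non-hematologic event possibly related to TMZ, except alopecia, "nausea and vomiting unless the subject has failed maximal antiemetic therapy, and fatigue".

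**Summary table**
- Delay row: "Non-hematologic (except alopecia, nausea/vomiting unless on maximal antiemetic therapy".
- Resume condition: non-hematologic events at Grade 1 or lower, with no exceptions listed.
- Stop row: "Non-hematologic (except alopecia, nausea/vomiting".

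The value column for both non-hematologic rows reads NA, so the table gives no grades. Section 8.3 adds that where local labelling conflicts with 8.3.1 or 8.3.2, "then either local prescribing information or protocol language can be used at the discretion of the investigator".

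**The concern.** These are working instructions, applied weekly to standard-of-care chemotherapy, and missed TMZ doses are not made up. A site that works from the table's labels with the text's grades would, for the same patient, do something different from a site that works from the text. It could hold or stop TMZ for fatigue that the text exempts. In the more serious direction, it would have no instruction to stop TMZ for severe vomiting after maximal antiemetics have failed.

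The text also has a fault of its own. One of its hold triggers is not matched by any recovery requirement, so that trigger achieves nothing.

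What is at stake is consistent safety management and, secondarily, the descriptive tables of TMZ doses in chemoradiation (SAP 9.2) and of TMZ discontinuations for adverse events (SAP 11.2).

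**Working it through.** No planned figure is involved, so the check compares the two rules case by case. All events are taken as possibly related to TMZ, with adequate counts. The grades come from the text, because the table gives none. N/V stands for nausea and vomiting.

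| Case | Text | Table |
|---|---|---|
| Grade 2 fatigue | continue | delay |
| Grade 3–4 fatigue | continue | stop |
| Grade 2 N/V, on maximal antiemetics | continue | delay |
| Grade 2 N/V, not on maximal antiemetics | hold | continue |
| Grade 3–4 N/V, maximal antiemetics failed | stop | not stopped |
| TMZ held for low platelets, now recovered; Grade 2 fatigue or N/V persists | resume | remain on hold |

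The rows reduce to four contradictions:
1. **Fatigue.** The text exempts it from hold, resume and stop. The table never does.
2. **Antiemetic clause for delay.** *While on* and *unless on* give opposite answers for both groups of patients.
3. **Stop.** The text stops TMZ once maximal antiemetics have failed. The table exempts N/V without condition.
4. **Resume.** The text excepts alopecia, N/V and fatigue. The table excepts nothing.

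**The hold that has no effect (text only).** Take Grade 2 N/V off maximal antiemetics, neutrophils at or above 1.5 × 10⁹/L, platelets at or above 100 × 10⁹/L, and no other event. The hold is triggered. The resume conditions are neutrophils at or above 1.5, platelets at or above 100, and no non-hematologic event above Grade 1 other than the excepted ones. N/V is excepted outright, so all three are already met when the hold begins. If another event or a low count is also present, that still keeps TMZ on hold. The setting is not exotic: section 5.3.1.1 says antiemetic prophylaxis is usually unnecessary with daily dosing, beyond the recommended first few doses.

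**Does anything settle text against table?** Section 8.3 ("then either local prescribing information or protocol language can be used at the discretion of the investigator") covers local labelling against the protocol. Sections 5.12.4 and 6.1.1 also point to local guidance. None says which part of 8.3.1 prevails.

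**Who could still be affected?**
- All 639 main-study subjects were enrolled by 19 March 2018 (SAP 6.0).
- Randomization may precede Day 1 by up to 3 days (Protocol 4.2), so the latest Day 1 is 19 + 3 = 22 March 2018.
- Concomitant TMZ lasts at most 49 days (Protocol 4.1), so Day 49 is 22 March + 48 days = 9 May 2018.
- The current synopsis is dated 26 May 2019. From 9 May 2018 that is 365 + 17 = 382 days.
- The Chinese cohort was still enrolling at the SAP date of 23 April 2019, and Appendix IX applies the main protocol's TMZ rules to the hepatic sub-study. Appendix X schedules post-radiation cycles only.

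**The case against.** The strongest reply is that the table calls itself a summary and cannot be used alone. Its non-hematologic rows carry neither a grade nor a relatedness condition, so a site must go to the text and will meet the full exceptions there. Local prescribing information (8.3 and 6.1.1) and the investigator's judgment of excessive toxicity (5.6) give further protection, particularly for severe vomiting. This stands as a limit on the likely consequence. It does not remove the contradiction, because nothing gives the text precedence.

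Three stronger readings are tempting, and the documents do not support them.

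- **The table's *unless on* is simply a misprint for *while on*.** The table's clause may be the intended one. With the text's stop rule it makes a sensible ladder: tolerate N/V until maximal antiemetics are in use, hold if it persists, stop at Grade 3–4 once they fail. The text's clause holds the undertreated patient and exempts the one still vomiting on full treatment. The documents do not decide between them.
- **The fatigue mismatch disadvantaged one arm.** Section 1.0 lists among the events with incidence at least 5% greater on ABT-414 "constipation, blood alkaline phosphatase increased, fatigue, and platelet count decreased". That list is for any grade over the whole study. The number with Grade 2 fatigue, related to TMZ and during chemoradiation, is not given, and fatigue is not among the Grade 3 or higher events listed as in excess. No arm imbalance in TMZ holds can be derived.
- **The text's hold lasts literally zero days.** Delays are decided weekly and non-hematologic events are assessed at least weekly, so a site might wait for the next assessment. The defensible statement is that the rule sets no recovery requirement for N/V.

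On fatigue, the adjuvant rules in 8.3.2 do not exempt it either, which resembles the table. However, the 8.3.1 text exempts fatigue in all three of its rules for this phase, which favours aligning the table to it.

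**Conclusion.** The inconsistency is real: four contradictions between text and table in 8.3.1, and one hold in the text that has no effect when N/V is its only trigger. None depends on the NA entries, which could come from the source or from text extraction.

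It is a minor fault in a safety rule. Overall survival, alpha and power are unaffected. The documents do not show that any patient was managed differently because of it, or that the arms differed. Main-study concomitant TMZ had ended by about 9 May 2018, taking enrolled to mean randomized. Only later Chinese-cohort or hepatic sub-study subjects could still meet these rules, and the documents do not show that any were in chemoradiation. Correction is still worthwhile, because an operative stop rule should not depend on which half of a section is read.

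**What to change.** 1. In the table's stop row, make the N/V exception fall away once the subject has failed maximal antiemetic therapy, as in the text.
2. Add fatigue to the exceptions in both non-hematologic table rows and in the table's resume condition. The resume condition should also carry the text's exception for alopecia.
3. Have the clinical leads choose one antiemetic clause for delay, *while on* or *unless on*, and use it in both text and table.
4. Make the N/V part of the resume condition, in text and table, match the chosen delay trigger, so that N/V which starts a hold must also recover before TMZ restarts.
5. Notify any site that still has subjects in chemoradiation.

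The cost is a few words in one table and one resume condition, one clinical decision, and a short notice if any such site exists. No new data, visits or analyses are needed.
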